### 7.2.4 Other allowed dose interruption for pembrolizumab

Pembrolizumab may be interrupted for situations other than treatment-related AEs such as medical / surgical events or logistical reasons not related to study therapy. Participants should be placed back on study therapy within 3 weeks of the scheduled interruption, unless otherwise discussed with the Sponsor. The reason for interruption should be documented in the patient's study record.

### 7.2.5 Dose Modification for Oxaliplatin, Cisplatin and TS-1

Please refer to criteria for oxaliplatin, cisplatin and TS-1 dose modification included in Table 7, Table 8, and Table 9, respectively.

Table 7 Dose Modification Guidelines for Oxaliplatin Drug-Related Adverse Events

Category	Toxicity	Hold Oxaliplatin Treatment for Grade	Timing for Restarting Oxaliplatin Treatment	Dose for Restarting Oxaliplatin Treatment
Hematologic 	Neutropenia 	2-3 	≥1,500/mm 	No Reduction If the criteria for starting the course are not met at Day 22, reduce by 1 DL.
		4 	≥1,500/mm 	Reduce by 1 DL
	Febrile neutropenia	3-4 	Toxicity resolves	Reduce by 1 DL
	Thrombocytopenia	2-4 	≥75,000/mm 	Reduce by 1 DL If a platelet count is ≥ 75,000/mm  to < 100,000/mm  at Day 22 
Non-hematologic	Creatinine increased	≥1.5 mg/dL 	<1.5 mg/dL	No reduction
	Peripheral sensory neuropathy 	2 May be interrupted at the discretion of the investigator 3-4 	Grade 0-2 Grade 0-2	Consider a reduction by 1 DL at the discretion of the investigator Reduce by 1 DL

 Subjects with intolerable or persistent Grade 2 drug-related AE may hold at physician discretion.  
 Permanent discontinuation should be considered for any severe or life-threatening event. Consult Sponsor before restarting treatment after Grade 4 drug-related AE.  
 If ≥75,000/mm^3 and < 100,000/mm^3 persist in the next and subsequent courses, a dose reduction is not mandatory.  
 Administration may be interrupted or reduced at the discretion of the investigator.  
 See the package insert of each G-CSF drugs for administration of G-CSF for neutropenia.

Table 8 Dose Modification Guidelines for Cisplatin Drug-Related Adverse Events

Category	Toxicity	Hold Cisplatin Treatment for Grade	Timing for Restarting Cisplatin Treatment	Dose for Restarting Cisplatin Treatment
Hematologic 	Neutropenia 	2-3 	≥1,500/mm 	No Reduction If the criteria for starting the course are not met at Day 22, reduce by 1 DL.
		4 	≥1,500/mm 	Reduce by 1 DL
	Febrile neutropenia	3-4 	Toxicity resolves	Reduce by 1 DL
	Thrombocytopenia	2	≥75,000/mm 	No Reduction
3-4 		≥75,000/mm 	Reduce by 1 DL	
Non-hematologic	Creatinine increased	>1.2 x ULN 	≤1.2 x ULN	Reduce by 1 DL
	Ototoxicity or Peripheral sensory neuropathy 	3-4 	Grade 0-2	Reduce by 1 DL

 Subjects with intolerable or persistent Grade 2 drug-related AE may hold at physician discretion.  
 Permanent discontinuation should be considered for any severe or life-threatening event. Consult Sponsor before restarting treatment after Grade 4 drug-related AE.  
 Administration may be interrupted or reduced at the discretion of the investigator.  
 See the package insert of each G-CSF drugs for administration of G-CSF for neutropenia.

Table 9 Dose Modification Guidelines for TS-1 Drug-Related Adverse Events

Category	Toxicity	Hold TS-1 Treatment for Grade	Timing for Restarting TS-1 Treatment	Dose for Restarting TS-1 Treatment
Hematologic 	Neutropenia 	3 	≥1,500/mm 	No Reduction If the criteria for starting the course are not met at Day 22, reduce by 1 DL.
		4 	≥1,500/mm 	Reduce by 1 DL
	Febrile neutropenia	3-4 	Toxicity resolves	Reduce by 1 DL
	Thrombocytopenia	3-4 	≥75,000/mm 	Reduce by 1 DL
Non-hematologic	Diarrhoea, Mucositis, or Hand and foot syndrome	2-4 	Grade 0-1	Reduce by 1 DL
	Creatinine increased	[Cohort 1] ≥1.5 mg/dL  [Cohort 2] > 1.2 x ULN 	[Cohort 1] <1.5 mg/dL [Cohort 2] ≤ 1.2 x ULN	No Reduction
	AST, ALT	> 2.5 x ULN  > 5 x ULN for subjects with liver metastases	≤ 2.5 x ULN ≤ 5 x ULN for subjects with liver metastases	Reduce by 1 DL

 Subjects with intolerable or persistent Grade 2 drug-related AE may hold at physician discretion.  
 Permanent discontinuation should be considered for any severe or life-threatening event. Consult Sponsor before restarting treatment after Grade 4 drug related AE.  
 See the package insert of each G-CSF drugs for administration of G-CSF for neutropenia.

## 7.2.6 Timing of Dose Administration

Study treatment in all the cohorts will begin on Day 1 of each 3-week dosing cycle after all procedures/assessments have been completed as detailed on the Trial Flow Chart (Section 6.0). Trial treatments may be administered up to 3 days before or after the scheduled Day 1 of each cycle due to administrative reasons.

All trial treatments may be administered on an outpatient basis.

Treatment will be administered in the order presented below:

- Pembrolizumab infusion is administered first followed by the oxaliplatin or cisplatin infusion and then TS-1 administration.
- Treatment may continue with pembrolizumab+chemotherapy until documented confirmed disease progression, unacceptable AE(s), intercurrent illness that prevents further administration of treatment, Investigator's decision to withdraw the subject, subject withdraws consent, subject's request to discontinue, pregnancy of the subject, noncompliance with trial treatment or procedure requirements, or administrative reasons requiring cessation of treatment, or until the participant has received 35 administrations of pembrolizumab (approximately 2 years).

Note: Dosing interruptions are permitted in the case of medical / surgical events or logistical reasons (i.e. elective surgery, unrelated medical events, subject vacation, and holidays) not related to study therapy. Subjects should be placed back on study therapy as soon as clinically appropriate per the investigator, and not exceeding 3 weeks from the interrupted dosing. For all study drugs, Day 1 of subsequent cycles should be adjusted accordingly to adhere to every 3 week dosing schedule. Discuss with the Sponsor if subjects cannot restart study medication within 3 weeks. The reason for interruption should be documented in the subject's study record.

### 7.2.6.1 Pembrolizumab

Regardless of clinical benefit, subjects may only receive 35 administrations (approximately 2 years) with pembrolizumab. Pembrolizumab 200 mg fixed dose will be administered as a 30 minute IV infusion Q3W. Sites should make every effort to target infusion timing to be as close to 30 minutes as possible. However, given the variability of infusion pumps from site to site, a window of -5 minutes and +10 minutes is permitted (i.e., infusion time is 30 minutes: -5 min/+10 min).

The Pharmacy Manual contains specific instructions for the preparation of the pembrolizumab infusion fluid and administration of infusion solution.

### 7.2.6.2 Oxaliplatin

Oxaliplatin 130 mg/m^2 will be administered as a 120 minute IV infusion Q3W on Day 1 of each treatment cycle after all procedures and assessments are completed according to the "TRIAL FLOW CHART in Section 6.0" and pembrolizumab infusion is completed. The administration of oxaliplatin may be interrupted or reduced at the discretion of the investigator because the incidence of neuropathy has been reported to increase with increases in the dose.

### **7.2.6.3 Cisplatin**

Cisplatin 60 mg/m^2 will be administered as over 120 minute (120 minute or more is recommended. If it is difficult due to the time, 60 minute or more is allowed.) IV infusion Q3W on Day 1 of each treatment cycle after all procedures and assessments are completed according to the “TRIAL FLOW CHART in Section 6.0” and pembrolizumab infusion is completed. The administration of cisplatin may be interrupted or reduced at the discretion of the investigator because the incidence of hearing impaired has been reported to increase with increases in the dose.

### **7.2.6.4 TS-1**

As tegafur, TS-1 40 to 60 mg/body/dose BID according to the BSA will be administered Q3W at Days 1 to 14 after completion of all procedures and assessments according to the “TRIAL FLOW CHART in Section 6.0,” and pembrolizumab and oxaliplatin or cisplatin infusion. An interval of at least 8 hours should be kept between the evening and morning doses of TS-1. The subjects should have a meal and take the drug within 60 minutes after the meal. For additional guidance on the treatment method of TS-1, see the package insert.

Note: If subject is enrolled later in the day, it is acceptable for only 1 dose taken on Day 1, and BID dosing can resume on Days 2-14 and the final dose will be taken in the morning of D15.

## **7.3 Method of Treatment Assignment**

Participants participating in this trial will be allocated by non-random assignment. The subjects will be enrolled in the study using web registration system (IWRS). There are 2 cohorts, and the first approximately 45 subjects will be assigned to Cohort 1. After enrollment in Cohort 1 is completed, enrollment in Cohort 2 will be started.

### **7.3.1 Stratification**

No stratification based on age, sex or other characteristics will be used in this study.

## **7.4 Blinding**

This study is an open-label trial; therefore, the Sponsor, investigator and participant will know the treatment administered.

## **7.5 Preparation/Handling/Storage/Accountability**

### **7.5.1 Dose Preparation**

Details on preparation and administration of pembrolizumab are provided in the Pharmacy Manual. Concomitant chemotherapeutic agents will be prepared and administered as per the approved product label(s).

## **7.5.2 Handling, Storage and Accountability**

The investigator or designee must confirm appropriate temperature conditions have been maintained during transit for all study treatment received and any discrepancies are reported and resolved before use of the study treatment.

Only participants enrolled in the study may receive study treatment and only authorized site staff may supply or administer study treatment. All study treatments must be stored in a secure, environmentally controlled, and monitored (manual or automated) area in accordance with the labeled storage conditions with access limited to the investigator and authorized site staff.

The investigator, institution, or the head of the medical institution (where applicable) is responsible for study treatment accountability, reconciliation, and record maintenance (ie, receipt, reconciliation, and final disposition records).

For all study sites, the local country Sponsor personnel or designee will provide appropriate documentation that must be completed for drug accountability and return, or local discard and destruction if appropriate. Where local discard and destruction is appropriate, the investigator is responsible for ensuring that a local discard/destruction procedure is documented.

The study site is responsible for recording the lot number, manufacturer, and expiry date for any locally purchased product as per local guidelines unless otherwise instructed by the Sponsor.

The investigator shall take responsibility for and shall take all steps to maintain appropriate records and ensure appropriate supply, storage, handling, distribution and usage of study treatments in accordance with the protocol and any applicable laws and regulations.

## **7.6 Treatment Compliance**

Interruptions from the protocol specified treatment plan for more than 12 weeks between pembrolizumab doses for non-drug-related or administrative reason require consultation between the investigator and the Sponsor and written documentation of the collaborative decision on participant management.

## **7.7 Concomitant Therapy**

### **7.7.1 Acceptable Concomitant Medications**

All treatments that the investigator considers necessary for a subject's welfare may be administered at the discretion of the investigator in keeping with the community standards of medical care. All concomitant medication will be recorded on the case report form (CRF) including all prescription, over-the-counter (OTC), herbal supplements, and IV medications and fluids.

All concomitant medications received during the trial through 30 days after the last dose of trial treatment should be recorded. Concomitant medications administered after 90 days after the last dose of trial treatment should be recorded for SAEs and ECIs as defined in Section 7.2.

### 7.7.2 Prohibited Concomitant Medication

Subjects are prohibited from receiving the following therapies during Screening to the day of Treatment discontinuation of this trial:

- Antineoplastic systemic chemotherapy or biological therapy not specified in the protocol
- Immunotherapy not specified in this protocol
- Investigational agents other than pembrolizumab
- Radiation therapy; palliative radiation therapy to a symptomatic lesion (e.g. bony metastasis), or to the brain may be permitted after consultation with the Sponsor.
- Live vaccines within 30 days prior to the first dose of trial treatment and while participating in the trial. Examples of live vaccines include, but are not limited to, the following: measles, mumps, rubella, chicken pox, yellow fever, rabies, BCG, and typhoid (oral) vaccine. The killed virus vaccines used for seasonal influenza vaccines for injection are allowed; however live attenuated intranasal influenza vaccines (e.g. Flu - Mist®) are not allowed.
- Systemic glucocorticoids for any purpose other than to modulate symptoms from an event of clinical interest of suspected immunologic etiology or cisplatin supportive care. The use of physiologic doses of corticosteroids may be approved after consultation with the Sponsor (e.g., for control of acute asthma symptoms).
- For subjects assigned to Cohort 2:
  - Phenytoin should not be started with cisplatin therapy.
- Flucytosine
- Tegafur/Uracil and calcium folinate

Subjects who, in the assessment by the investigator, require the use of any of the aforementioned treatments for clinical management should be removed from treatment. Subjects may receive other medications that the investigator deems to be medically necessary.

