## 5. Study Design

### 5.1 Overall Design

This is a nonrandomized, multi-site, open-label trial to estimate overall response rates (ORRs) of pembrolizumab + oxaliplatin + TS-1 and pembrolizumab + cisplatin + TS-1, as first-line treatment for gastric cancer in programmed death-ligand 1 (PD-L1) positive, human epidermal growth factor receptor 2 (HER2/neu) negative subjects with advanced gastric or gastroesophageal junction (GEJ) adenocarcinoma.

First, 45 subjects will be assigned to Cohort 1, pembrolizumab + oxaliplatin + TS-1 combination therapy, and then, 45 subjects will be assigned to Cohort 2, pembrolizumab + cisplatin + TS-1 combination therapy.

In all the Cohorts, the study treatment will be started at Day 1 of each 3-week course.

Table 1 Treatments Dose and Schedule

Cohort	Treatment Dose and Schedule
Cohort 1	Pembrolizumab 200 mg Q3W + oxaliplatin 130 mg/m  Q3W IV infusion + TS-1 BID continuous oral administration for 14 days followed by a recovery period of 7 days
Cohort 2	Pembrolizumab 200 mg Q3W + cisplatin 60 mg/m  Q3W IV infusion + TS-1 BID continuous oral administration for 14 days followed by a recovery period of 7 days

The body surface area [BSA (m^2)] should be calculated by the web registration system using the following DuBois formula:
 $BSA (m^2) = ([\text{body weight (kg)}]^{0.425} \times [\text{body height (cm)}]^{0.725}) \times 0.007184$ 
The administration of oxaliplatin may be interrupted or reduced at the discretion of the investigator because the incidence of neuropathy has been reported to increase with increases in the dose.
 
The administration of cisplatin may be interrupted or reduced at the discretion of the investigator because the incidence of hearing impaired has been reported to increase with increases in the dose.
	

The study treatment should be started within 8 days after the day of enrollment.

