#### 7.7.3.2 Supportive Care Guidelines for Oxaliplatin/ Cisplatin

Prevention and/or treatment of nausea and vomiting should be managed with:

1. IV EMEND (fosaprepitant) 150 mg IV or oral EMEND (aprepitant) 3 day pack 125 mg day 1, 80 mg day 2, 80 mg day 3
2. Plus Aloxi (Palonosetron) 0.25 mg IV

Nausea may also be managed with:

1. Zofran (Ondansetron) 8 mg twice a day
2. Or Compazine (Prochlorperazine) 10 mg 3-4 times per day

Additionally, use of steroids for oxaliplatin/ cisplatin associated anti-emetic support is allowed and is to follow the NCCN guideline, the local guidelines or institutional guidelines.

Please refer to the product label or local standards of care for additional oxaliplatin/ cisplatin supportive measures.

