## **10.9 Sample Size and Power Calculations**

A total of 80 subjects (TS-1 + oxaliplatin + pembrolizumab group [Cohort 1], 40 subjects; TS-1 + cisplatin + pembrolizumab group [Cohort 2], 40 subjects) will be included in the all participants as treated (ASaT). A total of 90 subjects (Cohort 1, 45 subjects; Cohort 2, 45 subjects) will be enrolled.

The sample size set with 90 subjects (Cohort 1 45 subjects; Cohort 2 45 subjects) that can expect a similar confidence interval of ORR to the previous studies of the first line treatment for gastric cancer for the purpose of the estimation of the ORR.

Considering approximately 10% of untreated subjects excluded, a total of 90 subjects (Cohort 1, 45 subjects; Cohort 2, 45 subjects) will be enrolled and a total of 80 subjects (Cohort 1, 40 subjects; Cohort 2, 40 subjects) will be included as ASaT.

[Table 15](#) show the two-sided 95% confidence interval of ORR when the number of subjects is 80 (40 subjects in Cohort 1 and 40 subjects in Cohort 2).

Table 15 Two sided 95% Confidence interval of ORR with 40 subjects as ASaT

Number of Observed Responders	ORR Estimates	95% CI of ORR (%)
16	40.0%	(24.9, 56.7)
17	42.5%	(27.9, 59.)
18	45.0%	(29.3, 61.5)
19	47.5%	(31.5, 63.9)
20	50.0%	(33.8, 66.2)
21	52.5%	(36.1, 68.5)
22	55.0%	(38.5, 70.7)
23	57.5%	(40.9, 73.0)
24	60.0%	(43.3, 75.1)
25	62.5%	(45.8, 77.3)
26	65.0%	(48.3, 79.4)
27	67.5%	(50.9, 81.4)
28	70.0%	(53.5, 83.4)
29	72.5%	(56.1, 85.4)
30	75.0%	(58.8, 87.3)
31	77.5%	(61.5, 89.2)
32	80.0%	(64.4, 90.9)

There will be approximately 40 subjects enrolled for each cohort, [Table 16](#) shows the two-sided 95% CI of AE rate with 40 subjects.

Table 16 Two-sided 95% CI of AE incidence rate with 40 Subjects

Number of AE	AE incidence rate estimates	95% CI of incidence rate (%)
1	2.5%	(0.00, 13.2)
2	5.0%	(0.61, 16.9)
3	7.5%	(1.57, 20.4)
4	10.0%	(2.8, 23.7)
5	12.5%	(4.2, 26.8)
6	15.0%	(5.7, 29.8)
7	17.5%	(7.3, 32.8)
8	20.0%	(9.1, 35.7)
9	22.5%	(10.8, 38.5)

Number of AE	AE incidence rate estimates	95% CI of incidence rate (%)
10	25.0%	(12.7, 41.2)
11	27.5%	(14.6, 43.9)
12	30.0%	(16.6, 46.5)
13	32.5%	(18.6, 49.1)
14	35.0%	(20.6, 51.7)
15	37.5%	(22.7, 54.2)

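### Sections 7.7.2 and 7.7.3.2 conflict on anti-emetic steroids with oxaliplatin, so a Cohort 1 subject can be compliant under one and liable to removal from treatment under the other

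*Combined protocol and SAP*

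**What the plan says.** Section 7.7.2 opens its list with "Subjects are prohibited from receiving the following therapies during Screening to the day of Treatment discontinuation of this trial". The steroid entry reads "Systemic glucocorticoids for any purpose other than to modulate symptoms from an event of clinical interest of suspected immunologic etiology or cisplatin supportive care". It goes on to say that physiologic doses may be approved after consultation with the Sponsor, with acute asthma as the example. After the list, the section says that subjects who, in the investigator's assessment, "require the use of any of the aforementioned treatments for clinical management should be removed from treatment".

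Section 7.7.3.2 covers supportive care for both platinum drugs. It names several non-steroid anti-emetics and then adds that "use of steroids for oxaliplatin/ cisplatin associated anti-emetic support is allowed and is to follow the NCCN guideline", or else local or institutional guidelines.

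Oxaliplatin is given only in Cohort 1. Section 5.1 states: "First, 45 subjects will be assigned to Cohort 1, pembrolizumab + oxaliplatin + TS-1 combination therapy". Section 7.2.6.2 places it on Day 1 of every 3-week cycle.

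**The concern.** The prohibited list exempts supportive care for one platinum drug. The supportive-care section exempts anti-emetic use for both. The mismatch falls on the cohort that receives the drug missing from 7.7.2, and on a use that is foreseeable enough for the protocol to have its own section on it.

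The stated consequence in 7.7.2 is more than a data query, since it provides for removal from treatment. One site could treat the same steroid dose as permitted care, another could log a deviation, and a third could withhold the steroid or stop treatment. That would put differences between sites, caused only by drafting, into Cohort 1's deviation counts, exposure summaries and reasons for discontinuation. Section 4 makes the number of participants stopping study drug because of adverse events a secondary safety outcome, and a removal prompted by vomiting could be recorded there. Section 5.4.2 explains that Cohort 1 is enrolled first because there were no safety data for pembrolizumab with oxaliplatin, so clean discontinuation data matter in this cohort.

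**Working it through.** No alpha, power or effect-size figure is involved. The check sets the two sections side by side and then counts who is under both.

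**1. Does a steroid given for oxaliplatin-related vomiting fit an exception in 7.7.2?** There are three.

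- Immunologic event of clinical interest: no, the purpose is different.
- Cisplatin supportive care: no, Cohort 1 does not receive cisplatin.
- Physiologic dose approved after Sponsor consultation: not in general. Section 7.7.3.2 permits guideline-based use and sets neither a physiologic-dose limit nor a consultation step.

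**2. Is the prohibition limited by cohort or by time?** It runs from Screening to treatment discontinuation, so it covers every oxaliplatin cycle. Where 7.7.2 means to limit an entry to one cohort it says so, as in its phenytoin entry for Cohort 2. The steroid entry has no such limit.

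**3. Does 7.7.3.2 cover the same use?** Yes. It says that "use of steroids for oxaliplatin/ cisplatin associated anti-emetic support is allowed".

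**4. Does other text settle the conflict?**

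- Section 7.7.1 gives the investigator general discretion over necessary treatments. It does not say that this overrides the specific prohibitions in the next section.
- The last sentence of 7.7.2 allows other medications judged necessary. Glucocorticoids are on the list, so they are not among the others.
- No section gives an order of precedence.

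**5. How many subjects are under both rules?** Section 10.9 plans 40 treated subjects per cohort: "Considering approximately 10% of untreated subjects excluded, a total of 90 subjects". The plan's enrolment figure reproduces:

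- 40 / (1 − 0.10) = 44.4, rounded up to 45 per cohort, and 2 × 45 = 90.
- Cohort 1 is 45 / 90 of those enrolled and 40 / 80 of those treated, half in each case.

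Untreated subjects receive no oxaliplatin, so the relevant ceiling is about 40 rather than 45. Steroids are permitted and not required, and the documents give no expected rate of use. The number for whom the conflict takes effect is therefore 0 to about 40.

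**6. Does removal from treatment translate into a lost response?** Not directly.

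- Section 8.1 says that stopping treatment is not withdrawal from the study.
- The Schedule of Activities (note b) and Sections 9.2.1.3 and 9.10.3.2 continue imaging every 6 weeks after discontinuation without progression. Section 9.2.1 sends scheduled images for all participants to blinded independent central review (BICR).
- A response seen before or after stopping can therefore still be confirmed. A loss needs a further step, such as a new anticancer therapy, which ends imaging under 9.2.1.3, or a response that does not occur because exposure was shorter.

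The documents give no rate for either step, so the effect on the response rate cannot be computed.

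**The case against.** The strongest reply is that 7.7.3.2 is the more specific text. It is headed for both platinum drugs and expressly permits the use, and 7.7.1 leaves necessary care to the investigator. On that reading a site would seldom stop treatment over a use the protocol allows, and the commoner result would be uneven deviation logging. This is plausible and tempers the expected effect. It does not remove the conflict. Section 7.7.2 is also specific, naming one platinum drug and leaving out the other, and a monitor working from the prohibited list has textual support for calling the use a deviation.

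Three stronger readings are tempting and are not supported.

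- A reader might infer that every Cohort 1 subject given an anti-emetic steroid must be removed. The sentence reaches only those who, in the investigator's judgement, require a listed therapy. Section 7.7.3.2 also offers non-steroid options and makes steroids optional.
- A reader might infer that each removal before confirmation, nominally 6 + 4 = 10 weeks after enrollment, costs Cohort 1 up to 1/40 = 2.5 points of response rate. Section 10.6.1 does count subjects without response data as non-responders. But stopping treatment does not by itself end imaging or central review, so the loss does not follow. Week 10 is not a firm minimum either, because the first scan has a window of 7 days either side and may be earlier if clinically indicated.
- A reader might infer a biased comparison between cohorts. The cohorts are sequential and non-randomised, the objectives apply to each separately, and no between-cohort test is planned. The effect lies within Cohort 1.

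**Conclusion.** The conflict is real and both passages are current text. For one foreseeable use, anti-emetic steroids with oxaliplatin, 7.7.3.2 gives permission while 7.7.2 gives a prohibition with a removal sentence. All treated Cohort 1 subjects, about 40 and half of the treated trial population, are under both rules. The number who would actually need such a steroid is not given.

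The expected consequence is inconsistency between sites in Cohort 1 in what is logged as a deviation, in anti-emetic use and in who stops treatment. How sites would in fact behave is an inference from the wording. Any effect on the response rate is indirect and unquantified, and no sample size, estimator or confidence interval depends on the point. It is an internal inconsistency that should be corrected because it bears on site conduct and costs little to repair.

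This conclusion assumes that the planned 40 treated subjects per cohort is met and that no site instruction outside these documents already settles the matter.

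**What to change.** Reconcile Sections 7.7.2 and 7.7.3.2 so that one list of permitted systemic steroid uses applies to each cohort, and word the removal sentence in 7.7.2 to refer to that list. Which uses belong on the list is the sponsor's clinical decision, and this review takes no position on it.

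The cost is about one sentence of protocol text and a notification to sites. Sample size, endpoints and analysis methods stay as they are.
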